The results from this study demonstrate that AT-10 administered in heavy smokers is safe and welltolerated. Addressing the primary objective, the pharmacodynamic analyses showed that AT-10 was generally similar to clopidogrel in its ability to inhibit platelet aggregation as evidenced by %IPA and %PRI assays (VASP). Therefore, the PD results suggest that AT-10 will provide clinically beneficial therapy in heavy smokers since there is no impact observed on %IPA using AT-10 with regard to smoking status. Finally, when compared to a similar study in non-smokers, AT-10 showed similar effects in smokers and non-smokers, while clopidogrel appeared to have higher exposure and enhanced inhibition of platelet aggregation in smokers. AT 10 was found to be safe and well tolerated in this study.

Conclusion:

Based on the results of nonclinical and clinical studies conducted so far, AT-10 was found to be safe, well tolerated and effective drug. And hence in order to further confirm its efficacy and safety in target populations and to overcome the limitations of existing drug i.e. Clopidogrel, further evaluation of AT-10 in Indian population is worth exploring.

[figure not shown]

Reference Product: Clopidogrel Bisulfate Tablet

Description:

Chemical Name: Hydrogen sulfate;hydron;methyl (2S)-2-(2-chlorophenyl)-2-(6,7-dihydro-4Hthieno[3,2-c]pyridin-5-yl)acetate

The chemical structure of Clopidogrel bisulfate is provided below.

Mechanism of Action:

Clopidogrel is an inhibitor of platelet activation and aggregation through the irreversible binding of its active metabolite to the P2Y12 class of ADP receptors on platelets.

Pharmacodynamics:

Clopidogrel must be metabolized by CYP450 enzymes to produce the active metabolite that inhibits platelet aggregation. The active metabolite of clopidogrel selectively inhibits the binding of adenosine diphosphate (ADP) to its platelet P2Y12 receptor and the subsequent ADP-mediated activation of the glycoprotein GP IIb/IIIa complex, thereby inhibiting platelet aggregation. This action is irreversible. Consequently, platelets exposed to clopidogrel's active metabolite are affected for the remainder of their lifespan (about 7 to 10 days). Platelet aggregation induced by agonists other than ADP is also inhibited by blocking the amplification of platelet activation by released ADP.

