6 STUDY OBJECTIVES AND RATIONALE

6.1 STUDY OBJECTIVES

Primary:

- To determine the safety and tolerability of AT -10 compared to Clopidogrel administered orally to humans.
- To compare effect of AT -10 (loading and maintenance doses) Vs approved doses of Clopidogrel (loading and maintenance doses) on platelet aggregation in poor and extensive metabolizers.
- To confirm the AT -10 loading dose (PD equivalent dose to the Clopidogrel 300 mg) and the AT -10 maintenance dose (PD equivalent to the Clopidogrel 75 mg) given as a loading dose followed by 5 days of maintenance dose

Secondary:

• To determine the single and multiple dose pharmacokinetics (PK) of Clopidogrel, AT -10, and active metabolite MP-H4.

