8.2 DISCONTINUATION AND WITHDRAWAL CRITERIA

- Subjects are free to withdraw from the study at any time without stating any reason.
- The investigator can withdraw a subject from the particular period or from the study if:
 - 1. The subject suffers from significant inter current illness or undergoes surgery during the study.
 - 2. The subject experiences an AE, when withdrawal would be in the best interest of the subject or subject experiences SAE will be withdrawn from the study unconditionally.
 - 3. The subject fails to comply with the requirements of the protocol.
 - 4. The subject tests positive for alcohol and/or drugs of abuse during the time of study period.
 - 5. The subject is found positive for Pregnancy test or becomes pregnant during the study.
 - 6. It is necessary to further protect the health of the subject or the integrity of the study.
 - 7. Any subject cross participates in other clinical study.
 - 8. The subject is found to hide important medical history which in opinion of Principal Investigator may compromise study objectives or his/her safety during participation in this study
 - 9. In Principal Investigator's opinion it is not in the subject's best interest to continue or any other justifiable reason, which should be adequately documented.

10. Sometimes, though rarely, the sponsor may stop the study.

Note:

- 1) No additional subjects will be enrolled to replace dropouts
- 2) Any subject who vomits within 2 hours after administration of study drug, the PK blood sampling for that period will be stopped and PK data will not be evaluated for PK; however, the pharmacodynamic assessments should be conducted. Vomiting early after administration of the test medication may decrease the bioavailability of the test drug. However, the subject may continue with subsequent periods (if any) of the study.
- 3) The final report will include reasons for withdrawal.
- 4) If any subject is withdrawn or dropped-out, subject's shall be requested for end of study safety assessment to ensure subject's safety. Subject withdrawal during the study shall be handled as per applicable SOPs with adequate documentation.

CONFIDENTIAL

Page 38 of 74

Ipca Laboratories Ltd Version 1.0 (Amendment 3.0)

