14.4 PHARMACODYNAMIC EFFECT ANALYSIS

ADP induced platelet aggregation will be assessed for change from baseline in each treatment group at each time point assessed on each dosing day (0.5, 2 and 6 hours post dose) and 24 hrs post dosing of last dosing day in each period. The change over time for each parameter will also be assessed.

Platelet inhibition will be calculated as per below formula.

Platelet Inhibition = $(1 - \text{Residual Impedance} / \text{Baseline Impedance}) \times 100$

The results will be reported as either residual platelet aggregation, measured as maximal amplitude of impedance (ohms), or platelet inhibition. The data from treatment groups 1 and 3 will be combined in the CONFIDENTIAL Page 63 of 74

analysis and similarly for treatment group 2 and 4 will be combined in the analysis. Statistical comparison will be made between the change from baseline at each time point between the treatment groups 1 and 3 (extensive metabolizers) versus treatment groups 2 and 4 (poor metabolizers) for each treatment (AT -10 and Clopidogrel). If applicable, as clinical phase of study will be conducted in group of volunteers not more than 18, volunteer group effect will also be analyzed statistically.

The incidence of signs of bleeding from the abbreviated physical examination and the incidence of abnormal liver function tests (ALT, AST, total bilirubin, and alkaline phosphatase) will be tabulated for the treatment groups. The incidence of these events will not be formally tested and the comparison will be observational only. The observational comparisons will be made between the AT -10 and Clopidogrel in the extensive metabolizers and poor metabolizers.

Additionally, the relationship between the PK of MP-H4 and pharmacodynamic measurements will be addressed using population PK-PD analysis.

CONFIDENTIAL

Page 64 of 74

Ipca Laboratories Ltd Version 1.0 (Amendment 3.0)

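### After a vomited dose, Note 2 of section 8.2 stops PK sampling for the period but continues platelet-aggregation assessment, so later PD values have no MP-H4 concentrations for the planned PK-PD analysis

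*Protocol*

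**What the plan says.** Note 2 in section 8.2 applies to vomiting within 2 hours of study drug. It says that "the PK blood sampling for that period will be stopped" and that "PK data will not be evaluated for PK; however, the pharmacodynamic assessments should be conducted". The reason it gives is "Vomiting early after administration of the test medication may decrease the bioavailability of the test drug". The subject may go on to the next period.

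Platelet aggregation belongs to the primary objectives. One of them in section 6.1 is "To compare effect of AT -10 (loading and maintenance doses) Vs approved doses of Clopidogrel". PK is the secondary objective.

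Section 14.4 says "ADP induced platelet aggregation will be assessed for change from baseline in each treatment group at each time point assessed on each dosing day". It names no special handling for values after a vomited dose. It also says that "the relationship between the PK of MP-H4 and pharmacodynamic measurements will be addressed using population PK-PD analysis".

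Section 13 has every available plasma sample assayed, so samples drawn before the vomit still yield concentrations.

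**The concern.** Note 2 doubts the dose because absorption may be reduced. That doubt applies equally to platelet inhibition, which depends on the active metabolite formed from the absorbed drug. The rule ends the measurements that would show how much was absorbed and keeps the measurements whose interpretation depends on that amount.

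The timing makes this matter. For clopidogrel, section 5 puts the active metabolite's peak at about 30 to 60 minutes after dosing and its half-life at about 30 minutes. A subject who vomits after 20 minutes and one who vomits after 1 hour 50 minutes may have had very different exposures. The remaining scheduled samples would help to tell them apart, and Note 2 cancels them.

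The stop covers the whole period. PD values on later days, after further doses, therefore also lack MP-H4 concentrations. What is at stake is the PK-PD analysis in section 14.4, which loses exposure data in the subjects most likely to have low exposure, and the ability to interpret those subjects' aggregation results.

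**Working it through.** **Inputs.** Sampling times are from sections 9.2.6 (PK) and 11.2 (PD). Blood volumes are from the table in section 9.2.6. Stratum size is 20 (section 7.1), with no replacement of dropouts (section 8.2, Note 1).

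**1. Sample counts per period, checked against the protocol's own volumes.**

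- PK: 13 on Day 1 (pre-dose and 12 later times, the last at 24 h), 3 pre-dose samples on Days 3 to 5, and 13 on Day 6. Total 13 + 3 + 13 = 29.
- PK volume: 29 × 5 mL × 2 periods = 290 mL. The table states 290 mL.
- PD: 4 on each of 6 days plus one at 24 h after the last dose. Total 6 × 4 + 1 = 25.
- PD volume: 25 × 2.7 mL × 2 periods = 135 mL. The table states 135 mL.

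Both volumes reproduce exactly, so the counts are right.

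**2. What Note 2 removes after a vomit on Day 1.**

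- Vomit before 0.25 h: only the pre-dose PK sample has been drawn, so 29 − 1 = 28 are never drawn.
- Vomit at 2 h, with the 2 h sample already taken: 7 have been drawn (pre-dose, 0.25, 0.5, 0.75, 1, 1.5, 2 h), so 29 − 7 = 22 are never drawn.
- The 1 to 7 samples already drawn are assayed but barred from PK evaluation.
- PD: all 25 samples are still scheduled, and 25 − 1 = 24 of them follow the Day 1 dose.

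**3. The same rule after a vomit on Day 6.**

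- PK samples already drawn: 13 + 3 + 1 = 17 (vomit before 0.25 h) to 13 + 3 + 7 = 23 (vomit at 2 h).
- Never drawn: 29 − 17 = 12 down to 29 − 23 = 6.

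The loss of paired data is therefore greatest for an early vomit of the loading dose.

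**4. Illustration of the effect on a mean.** The protocol gives no vomiting rate, no share of effect lost and no PD standard deviation. Assume that one of the 20 subjects in a metabolizer stratum is affected, that true inhibition is 40-60% (the steady-state range that section 5 quotes for clopidogrel 75 mg), and that 25-100% of the effect is lost.

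Shift in the stratum mean = number affected × inhibition × share lost / 20.

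- Smallest: 1 × 40 × 0.25 / 20 = 0.5 points.
- Largest: 1 × 60 × 1.00 / 20 = 3.0 points.

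This applies only at the affected times, and only if those values are pooled with the rest.

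**The case against.** A reader might infer that the primary PD comparison counts a vomited dose as a full dose. The documents do not say so. Note 2 tells the site to carry out the PD assessments, which is an instruction to collect. Section 14.4 is silent on the PD analysis set, and a statistical analysis plan that is not at hand may define one. Continued PD collection is not an error either, since it leaves open both an all-data analysis and one without the affected values.

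A reader might also infer that these PD values have no MP-H4 exposure at all. That goes too far. Samples drawn before the vomit are assayed, and a vomit near 2 hours follows draws that span the expected peak for clopidogrel. The note bars evaluation for PK and does not expressly bar use in the PK-PD analysis. What is lost is all later sampling in the period.

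A definite bias, or wider intervals for a paired drug difference, is likewise unsupported. The statistical comparison that section 14.4 spells out is extensive versus poor metabolizers within each treatment, and the sample size in section 8 is expressly not based on PD effect. The steady-state inhibition figure may not describe a lost loading dose. Section 5 also has daily 75 mg clopidogrel inhibiting aggregation from the first day and reaching steady state between Day 3 and Day 7, so later values may partly or largely recover. Because the effect on platelets is irreversible, one lost maintenance dose should disturb aggregation much less than that day's PK profile, so some difference in handling is defensible.

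These objections limit what can be claimed about bias. They do not answer the loss of later PK samples, which no analysis plan can restore.

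**Conclusion.** The point holds as a mismatch between two stated rules. Note 2 ends PK sampling for the period while PD continues, and section 14.4 needs MP-H4 concentrations alongside PD. After a Day 1 vomit, the cost is 22 to 28 of 29 PK samples in that subject's period, with up to 24 of 25 PD samples taken after the dose. These counts rest only on the protocol's schedule and agree with its blood volumes.

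The effect on the aggregation comparisons cannot be sized from the documents. The 0.5 to 3.0 points is an illustration that depends on one affected subject of 20, the assumed inhibition and the assumed loss. If nobody vomits within 2 hours of a dose, nothing is lost. The change is worth making because it is cheap and the missing samples cannot be recovered afterwards.

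**What to change.** Amend Note 2 and section 14.4 as follows.

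1. Replace the instruction to stop PK sampling with one to take and assay the remaining scheduled samples after a vomit.
2. State that affected profiles may still be left out of the noncompartmental PK comparisons, but that their MP-H4 concentrations are used in the population PK-PD analysis with the matching PD values.
3. Flag PD values after a vomited dose and report the platelet-aggregation comparisons with and without them. Which is the main analysis can be left to the statistical analysis plan. Removing every PD value from the vomit to the end of the period as the main analysis would be a debatable exclusion after randomization. After a Day 1 vomit it would also drop values that follow retained maintenance doses.

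The cost is the already scheduled draws and assays in the few subjects affected, plus one extra analysis. The draws are within the 290 mL PK allowance in section 9.2.6, so no new procedure or blood volume is needed.

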8.3 DATA COLLECTION AND FOLLOW-UP FOR DISCONTINUED SUBJECTS

Investigator should try to obtain the reason, if subject withdraws his/her consent. Reason for withdrawal from the study shall be documented, whenever possible. Post-study safety follow-up shall be performed for all prematurely discontinued subjects as per discretion of the investigator. For all discontinued subjects, data collected till the time of discontinuation shall be reported in CRF. Safety data shall be collected for all discontinued subjects, who are discontinued due to an adverse event (AE) or serious adverse event (SAE). In any case, every effort must be made to undertake protocol-specified safety follow-up procedures. If the subject is discontinued due to an event, he/she should be given an appropriate care under medical supervision until the symptoms of any AE resolve or the subject's condition becomes stable.

Ipca Laboratories Ltd Version 1.0 (Amendment 3.0)

9 STUDY SCHEDULE AND PROCEDURES

		Study Pe	eriods (Period 1	End of	
Procedure	Screening	Housing	Day 1 to 6	Day 7	study safety assessment
Informed Consent					
Inclusion Exclusion Criteria check		\checkmark			
Demographics and	,				
medication, medical					
History					
Vital Signs				V	
Clinical Examination					
CYP2C19	\checkmark				
genotyping		,			
Haematology					
Biochemistry	V				
Serology					
Liver function tests				\checkmark	
Urine analysis					
Coagulation		2	\checkmark		N
parameters	N	,	v	v	v
Urine pregnancy test					
and beta hCG test					
(only for female	, ,	v			v
subjects)					
12 Lead ECG					
Chest X-ray					
Urine drug screen for	2				
drugs of abuse	•	•			
Breath alcohol test					
IP Administration					
PK Blood Sampling					
PD Blood Sampling				\checkmark	
Abbreviated physical					
examination			Ň	v	v
Meal					
Discharge					
Monitoring and					
capturing of AE/SAE		V	٧	v	v

Ipca Laboratories Ltd Version 1.0 (Amendment 3.0)

9.1 SCREENING (DAY -28 TO -1)

- Written informed consent will be taken from the subject. No study related procedure will be conducted prior to obtaining written informed consent.
- CYP2C19 genotyping for classifying the subject as extensive (normal) metabolizer (for group 1 and 3) or poor metabolizer (for group 2 and 4) and informed consent during screening will be obtained from the volunteer before genotyping.
- Assessment of subject eligibility as per Inclusion and Exclusion criteria.
- Demographics (Such as Height, Weight, BMI, Age, Sex, Race, Ethnicity etc.)
- Clinical examination (including abbreviated physical examination focused on signs of bleeding including but not limited to echymosis, petechiae, and bleeding gums)
- Vital signs (including sitting blood pressure, pulse rate, respiratory rate and oral body temperature) after sitting for at least 3 minutes
- Prior medical history
- Medication history- The medication history of the subject must be recorded of at least 8 weeks prior to the screening visit.
- 12-Lead ECG
- Chest X-ray: X-ray done within 6 months of first dosing will be considered
- Clinical laboratory investigations (Hematology, Biochemistry including liver function tests, Serology)
- Coagulation parameters (PT and PTT) test
- Urine analysis (including urine pregnancy test)
- Beta hCG test (only for female subjects)
- Urine drug screen for drugs of abuse
- Breath Alcohol test

The site will carry out general screening with CYP2C19 based genotyping, so that site will have database of volunteers in sufficient number who are extensive (normal) metabolizers and poor metabolizers.

9.2 STUDY PERIOD

Housing (both periods) (Day (-1)):

- Evaluation as per inclusion/exclusion criteria
- A baseline 12-lead ECG will be performed.
- Clinical laboratory investigations (Hematology, Biochemistry including liver function tests)
- Urine analysis
- Coagulation parameters (PT and PTT) test
- Vital sign assessment (blood pressure, pulse rate, oral temperature, respiratory rate)
- Clinical examination (including abbreviated physical examination focused on signs of bleeding including but not limited to echymosis, petechiae, and bleeding gums)
- Urine pregnancy test and beta hCG test (only for female subjects)
- Urine drug screen for drugs of abuse

CONFIDENTIAL

Page 41 of 74

Ipca Laboratories Ltd Version 1.0 (Amendment 3.0)

- Breath alcohol test
- Monitoring and capturing of AE/SAE

Day 1 (both periods):

- Cannulation
- IP administration as per randomization
- PK blood sampling
- PD blood sampling
- Vital signs examination
- Abbreviated physical examination focused on signs of bleeding including but not limited to echymosis, petechiae, and bleeding gums
- Coagulation parameters (PT and PTT) test at 8 hr
- Meal at appropriate time (lunch, evening snacks, dinner)
- Monitoring and capturing of AE/SAE

Day 2 (both periods):

- IP administration
- PK blood sampling
- PD blood sampling
- Vital signs examination
- Abbreviated physical examination focused on signs of bleeding including but not limited to echymosis, petechiae, and bleeding gums
- Coagulation parameters (PT and PTT) test at 8 hr
- Meal at appropriate time (lunch, evening snacks, dinner)
- Monitoring and capturing of AE/SAE

Day 3 (both periods):

- IP administration
- PK blood sampling
- PD blood sampling
- Vital signs examination
- Abbreviated physical examination focused on signs of bleeding including but not limited to echymosis, petechiae, and bleeding gums
- Coagulation parameters (PT and PTT) test at 8 hr
- Meal at appropriate time (lunch, evening snacks, dinner)
- Monitoring and capturing of AE/SAE

Day 4 (both periods):

- IP administration
- PK blood sampling
- PD blood sampling
- Vital signs examination

CONFIDENTIAL

Page 42 of 74

Ipca Laboratories Ltd Version 1.0 (Amendment 3.0)

- Abbreviated physical examination focused on signs of bleeding including but not limited to echymosis, petechiae, and bleeding gums
- Coagulation parameters (PT and PTT) test at 8 hr
- Meal at appropriate time (lunch, evening snacks, dinner)
- Monitoring and capturing of AE/SAE

Day 5 (both periods):

- IP administration
- PK blood sampling
- PD blood sampling
- Vital signs examination
- Abbreviated physical examination focused on signs of bleeding including but not limited to echymosis, petechiae, and bleeding gums
- Coagulation parameters (PT and PTT) test at 8 hr
- Meal at appropriate time (lunch, evening snacks, dinner)
- Monitoring and capturing of AE/SAE

Day 6 (both periods):

- Cannulation
- IP administration
- PK blood sampling (Serial)
- PD blood sampling
- Vital signs examination
- Abbreviated physical examination focused on signs of bleeding including but not limited to echymosis, petechiae, and bleeding gums
- Coagulation parameters (PT and PTT) test at 8 hr
- Meal at appropriate time (lunch, evening snacks, dinner)
- Monitoring and capturing of AE/SAE

Day 7 (both periods):

- Last PK and PD blood sampling
- Safety assessment as follow
 - ✓ Clinical laboratory test (Hematology, Liver function test, Coagulation parameters (PT and PTT))
 - ✓ Vital sign assessment (blood pressure, pulse rate, oral temperature, respiratory rate)
 - ✓ Clinical examination (including abbreviated physical examination focused on signs of bleeding including but not limited to echymosis, petechiae, and bleeding gums)
- Discharge from the facility
- Monitoring and capturing of AE/SAE

End of Study Safety Assessment / Early Termination procedures:

• Safety assessment as follow

CONFIDENTIAL

Page 43 of 74

- Clinical laboratory test (Hematology, Biochemistry, Liver function test, Coagulation parameters (PT and PTT))
- Urine analysis
- Urine pregnancy test and beta hCG test (only for female subjects)
- Vital sign assessment (blood pressure, pulse rate, oral temperature, respiratory rate)
- Clinical examination (including abbreviated physical examination focused on signs of bleeding including but not limited to echymosis, petechiae, and bleeding gums)
- 12 lead ECG
- Monitoring and capturing of AE/SAE
- The subjects will then be discharged from the study center.

9.2.1 HOUSING

In both periods, subjects will be housed in the clinical study facility for at least 11.00 hours before administration of the IP and will continue to remain in the clinical study facility for at least 24.00 hours after administration of the last maintenance dose of IP.

A washout period of at least 14 days will be maintained between the study periods.

The subjects will be housed in a batch of not more than 18 subjects. Only one gender subject will be housed in one clinical ward. The study will be conducted in batches of subjects as per availability of subjects.

An example: Following may be the suggested plan of clinical conduct of study for various groups in different batches.

Group	Day 1-7	Day 8-14	Day 21-27	Day 28-34	Day 1-7	Day 8-14	Day 21-27	Day 28-34
Group-1 Males	P-I		P-II					
Group-2 Males	P-I		P-II					
Group-1 Females		P-I		P-II				
Group-2 Females		P-I		P-II				
Group-3 Males					P-I		P-II	
Group-4 Males					P-I		P-II	
Group-3 Females						P-I		P-II
Group-4 Females						P-I		P-II

P-I = Period 1, P-II = Period 2

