7 STUDY DESIGN

7.1 Design

This study is an open label, two-period, crossover study wherein each subject will receive a single loading dose followed by 5 daily doses (maintenance dose) of either AT-10 or Clopidogrel in Period 1 and then crossover to receive the other therapy (AT -10 or Clopidogrel) in Period 2.

40 subjects are planned to be randomized into the study. Out of this, 20 subjects would be extensive CYP2C19 metabolizers and 20 would be poor CYP2C19 metabolizers. The 20 extensive metabolizers will be randomized on a 1:1 basis into Groups 1 and 3. The 20 poor metabolizers will be randomized on a 1:1 basis into Groups 2 and 4. Subjects who withdraw or are removed from the study will not be replaced.

The dosing scheme is as follows:

Group & Sequence	Period 1	Period 2	
Group 1	AT -10 40mg on Day 1	Clopidogrel 300 mg on Day 1	
(n=10, extensive metabolizers)	AT -10 10 mg on Days, 2, 3, 4, 5 & 6	Clopidogrel 75 mg on Days 2, 3, 4, 5 & 6	
Sequence 1			
Group 2	AT -10 40 mg on Day 1	Clopidogrel 300 mg on Day 1	
(n=10, poor metabolizers)	AT -10 10 mg on Days, 2, 3, 4, 5,	Clopidogrel 75 mg on Days 2, 3,	
Sequence 1	& 6	4, 5 & 6	
Group 3	Clopidogrel 300 mg on Day 1	AT -10 40 mg on Day 1	
(n=10, extensive metabolizers)	Clopidogrel 75 mg on Days 2, 3, 4, 5, & 6	AT -10 10 mg on Days 2, 3, 4, 5 & 6	
Sequence 2			
Group 4	Clopidogrel 300 mg on Day 1	AT -10 40 mg on Day 1	
(n=10, poor metabolizers)	Clopidogrel 75 mg on Days 2, 3, 4,	AT -10 10 mg on Days 2, 3, 4, 5	
Sequence 2	5, & 6	& 6	

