9.2.2 INVESTIGATIONAL PRODUCT ADMINISTRATION

The randomization will be generated of #40 subjects for each type of metabolizers i.e. extensive and poor, and it will be for each gender group i.e. #20 for each male and female respectively for each type of metabolizers. Total 04 randomization schedule will be prepared. Each randomization schedule should be containing 20 subjects (10 subjects for each sequence). This randomization approach will help in achieving near to equal proportionate distribution of the treatment across the study and between the gender.

CONFIDENTIAL

Page 44 of 74

Ipca Laboratories Ltd Version 1.0 (Amendment 3.0)

As per randomization, IP will be administered as per below scheme on day 1, 2, 3, 4, 5 and 6 in each period. Subjects will be fasting overnight for at least 10.00 hours before IP administration. IP will be administered orally in sitting posture with 240 ± 2 mL of water at room temperature.

Group &	Period 1	Period 2
Sequence		
Group 1	AT -10 40mg on Day 1	Clopidogrel 300 mg on Day 1
(n=10, extensive	AT -10 10 mg on Days, 2, 3, 4, 5 & 6	Clopidogrel 75 mg on Days 2, 3, 4, 5
metabolizers)		& 6
Sequence 1		
Group 2	AT -10 40 mg on Day 1	Clopidogrel 300 mg on Day 1
(n=10, poor	AT -10 10 mg on Days, 2, 3, 4, 5, & 6	Clopidogrel 75 mg on Days 2, 3, 4, 5
metabolizers)		& 6
Sequence 1		
Group 3	Clopidogrel 300 mg on Day 1	AT -10 40 mg on Day 1
(n=10, extensive	Clopidogrel 75 mg on Days 2, 3, 4, 5,	AT -10 10 mg on Days 2, 3, 4, 5 & 6
metabolizers)	& 6	
Sequence 2		
Group 4	Clopidogrel 300 mg on Day 1	AT -10 40 mg on Day 1
(n=10, poor	Clopidogrel 75 mg on Days 2, 3, 4, 5,	AT -10 10 mg on Days 2, 3, 4, 5 & 6
metabolizers)	& 6	
Sequence 2		

Note: In all the periods, IP administration will be done by trained study personnel delegated by the investigator and will be reviewed by quality control / quality assurance personnel. Investigator will be available at site during IP administration. Subjects will be asked to swallow the tablet as a whole without being chewed, crushed or bitten. The time of dosing on Day 01 will be the reference time for all subsequent dosing. Dose 02 to Dose 06 will be administered at an interval of 24 hours of previous dose.

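### If the example batch plan is run as separate calendar blocks, each batch holds one sequence, and unequal calendar shifts can bias AT-10 versus clopidogrel

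*Protocol*

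**What the plan says.** Protocol 7.1 sets the allocation: "The 20 extensive metabolizers will be randomized on a 1:1 basis into Groups 1 and 3", and "The 20 poor metabolizers will be randomized on a 1:1 basis into Groups 2 and 4". In the dosing scheme of 9.2.2, Groups 1 and 2 (Sequence 1) start Period 1 with "AT -10 40mg on Day 1" and Groups 3 and 4 (Sequence 2) with "Clopidogrel 300 mg on Day 1". The same section prepares four randomisation schedules, by sex and metabolizer type. Their stated aim is to spread treatment about evenly over the study and between the sexes.

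On conduct, 9.2.1 says: "The subjects will be housed in a batch of not more than 18 subjects". Each ward houses one gender. It adds: "The study will be conducted in batches of subjects as per availability of subjects". An example table follows, introduced by "Following may be the suggested plan of clinical conduct of study for various groups in different batches". Groups 1 and 2 fill the first four day columns, and Groups 3 and 4 fill a second set of four with the same day labels. Within each set, men and women are in different weeks.

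Section 14.4 adds that, if applicable, "volunteer group effect will also be analyzed statistically". No section says that a batch must contain both sequences.

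**The concern.** A two-period crossover removes period effects from the treatment comparison because both sequences pass through the same periods. If all AT-10-first subjects are dosed in one stretch of the calendar and all clopidogrel-first subjects in another, Period 1 of one sequence and Period 1 of the other are different weeks. What changes between those weeks (reagent lot, instrument, operator) no longer cancels automatically.

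The most exposed endpoint is ADP-induced aggregation, which is analysed at the site (11.2). It carries two primary objectives in 6.1: comparing AT-10 with clopidogrel on platelet aggregation, and confirming the AT-10 doses as pharmacodynamically equivalent. The layout also sits badly with the aim in 9.2.2 of an even spread of treatment across the study. And if volunteers are not randomised before they are scheduled, filling single-sequence blocks by availability could tie a volunteer's sequence to when he or she can attend.

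**Working it through.** The protocol states no figure to reproduce, so this is a check of structure. Inputs from the protocol: the 9.2.1 table, the sequences in 9.2.2, and 40 subjects in four groups of 10. Assumptions: five men and five women per group, and the two column sets read as separate calendar blocks A (Groups 1, 2) and B (Groups 3, 4).

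**Batch by sequence**

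| Batch | Sequence 1 | Sequence 2 | Period 1 drug | Period 2 drug |
|---|---|---|---|---|
| Men, Groups 1+2 | 10 | 0 | AT-10 | clopidogrel |
| Women, Groups 1+2 | 10 | 0 | AT-10 | clopidogrel |
| Men, Groups 3+4 | 0 | 10 | clopidogrel | AT-10 |
| Women, Groups 3+4 | 0 | 10 | clopidogrel | AT-10 |

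All eight housing weeks have a single drug. Four batches have 3 degrees of freedom: sex takes 1, sequence 1 and sex by sequence 1, leaving 0 for a separate volunteer group effect.

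**Estimability.** Treatment can be estimated if adding it raises the rank of the design matrix.
- Subject + period: 41 to 42, estimable.
- Subject + calendar week: 44 to 44, not estimable.
- Subject + batch-by-period: not estimable.
- Subject + calendar week, with both sequences in each of four batches: 44 to 45, estimable.

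**Bias.** Let tau be the AT-10 minus clopidogrel effect, and piA1, piA2, piB1, piB2 the period levels in the two blocks.
- Sequence 1, Period 1 minus Period 2: tau + (piA1 - piA2).
- Sequence 2, Period 2 minus Period 1: tau - (piB1 - piB2).
- Average: tau + 0.5 × [(piA1 - piA2) - (piB1 - piB2)].

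The second term does not depend on the number of subjects. For illustration only, a 10-unit shift in one block and none in the other gives 0.5 × 10 = 5 units.

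**What cancels.** A constant batch effect cancels within subject. So does steady linear drift: both blocks have men at Day 1 and Day 21 and women at Day 8 and Day 28, so the spacing is 20 days throughout. A slope b per day gives 0.5 × [(-20b) - (-20b)] = 0. Only unequal, non-linear shifts do harm.

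**Sensitivity to assumed week effects.** The standard crossover t-test was simulated 4,000 times per setting, with within-subject SD 1, independent week effects, no true treatment difference and no baseline correction. The mixed-sequence batches simulated were two of 12 and two of 8.

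| Week SD ÷ within-subject SD | Example plan | Both sequences in each batch |
|---|---|---|
| 0 | 0.050 | 0.048 |
| 0.25 | 0.109 | 0.041 |
| 0.5 | 0.251 | 0.032 |
| 1 | 0.453 | 0.016 |

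Hand check at 0.5, for one sequence mean of 20 subjects in two batches:
- True variance: 2/20 + (2 × 0.25)/2 = 0.35.
- Variance the test expects: (2 + 5/19)/20 = 0.113, since the between-batch sum of squares averages 5.
- Effective critical value: 2.02 × sqrt(0.113/0.35) = 1.15, a two-sided error of about 0.25, as simulated.

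The mixed design falls below 0.05 because week variation sits in the residual; period-within-batch terms would remove it.

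**The case against.** The strongest reply is that the table is an illustration. The operative rules are the 1:1 randomisation in 7.1 and the schedules in 9.2.2. That stands: the defect is an unsuitable example that no other rule corrects, not a fixed schedule.

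Separate calendar blocks are the natural reading of the layout, but no dates are given and both column sets carry the same day labels. If they ran concurrently, every week would have both drugs and treatment would be estimable with calendar week fitted (rank 42 to 43). At an even split that puts 20 subjects of one gender in house, above 18 if they formed one batch, though separate batches would avoid this. The point is therefore conditional.

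A reader might infer that filling batches by availability defeats the randomisation. The protocol does not say so. It plans a genotyped volunteer database (8, 9.1) and does not state whether randomising or batching comes first. Randomising all 40 beforehand would remove the link. It would strain the Day -28 to -1 screening window if block B began after Day 34, so a risk remains, but only a risk.

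A reader might also infer that all comparisons are spoiled. The statistical PD comparison that 14.4 describes is extensive versus poor metabolizers within each treatment. Each batch in the table pairs an extensive with a poor group, so that contrast is balanced within batch. PK plasma is shipped and assayed at a separate laboratory (9.2.7, 13), and nothing ties assay runs to clinic weeks, so harm to PK is not shown.

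Finally, same-period baselines help. Percent inhibition is a ratio of residual to baseline impedance (14.4), so a proportional shift common to both readings cancels if the baseline is taken in the same period. Additive shifts, and changes during the dosing week after the baseline, would not cancel fully.

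**Conclusion.** The concern holds conditionally. If the example is followed as separate calendar blocks, sequence and batch cannot be told apart, the volunteer group effect cannot be isolated, and AT-10 versus clopidogrel depends on the two blocks having equal period shifts. The bias is half the difference between those shifts.

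Its size is unknown, because the protocol gives no week-to-week variation for aggregometry. The rejection rates of 0.109 to 0.453 rest on assumed week SDs, an assumed even sex split and no baseline correction; they show sensitivity and do not predict this trial. Since treatment drops out of any model with calendar week or batch-by-period terms, analysis cannot repair the layout afterwards. It should be settled before enrolment.

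**What to change.** Replace the example table in 9.2.1 with a rule: every housing batch contains both sequences in near-equal numbers for each genotype present (Group 1 with Group 3, Group 2 with Group 4), within the 18-subject cap and one-gender wards. At an even split, two male and two female batches of about 10 satisfy this. Putting all men in one batch would not, since 20 exceeds 18.

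Assign volunteers to a batch first and randomise sequence within batch, extending the four schedules in 9.2.2 accordingly. Include batch and period-within-batch terms in the AT-10 versus clopidogrel analysis, so that the volunteer group effect in 14.4 can be estimated separately from sequence.

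The number of batches stays at four, with no extra subjects or bed-days. The schedules must be regenerated, and two products are dispensed on the same ward day. The individually labelled containers and tear-off labels in 10.3 already control that.
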